#### Pregnancies

Any pregnancy that occurs during study participation should be reported. To ensure patient safety each pregnancy must also be reported to Novartis within 24 hours of learning of its occurrence. The pregnancy should be followed up to determine outcome, including spontaneous or voluntary termination, details of the birth, and the presence or absence of any birth defects, congenital abnormalities, or maternal and/or newborn complications.

#### 8.2 Clinical Laboratory Adverse Events

The results of all laboratory tests required by the protocol will be recorded in the patient's medical record. All clinically important abnormal laboratory tests occurring during the study will be repeated at appropriate intervals until they return either to baseline or to a level deemed acceptable by the investigator and the diagnosis that explains them is made.

The criteria for determining whether an abnormal laboratory test result should be reported as an adverse event are as follows:

- 1. Test result is associated with accompanying symptoms, and/or
- 2. Test result requires additional diagnostic testing or medical/surgical intervention, and/or
- 3. Test result leads to a change in study dosing or discontinuation from the study, significant additional concomitant drug treatment or other therapy, and/or
- 4. Test result leads to any of the outcomes included in the definition of a SAE, and/or
- 5. Test result is considered to be an adverse event by the investigator.

\*Merely repeating an abnormal test, in the absence of any of the above conditions, does not meet Condition 2 above for reporting as an adverse event.

Any abnormal test result that is determined to be an error does not require reporting as an adverse event, even if it did meet one of the above conditions except for Condition 4.

### 8.3 Management of Persistent and Refractory Toxicity

Utilizing the NCI CTCAE (version 4.0), events which are moderate and interfere with function that are not consistent with a patient's medical history, and are refractory to medical treatment, should be investigated carefully to ensure that no other etiology is present. Study drug will be held for any toxicity events deemed definitely, probably, or possibly drug-related (such as diarrhea, hypertension, vomiting, diarrhea, and dizziness) and that are greater than grade 2. Drug will be held until severity is reduced to Grade 1

Protocol 2011-0465 ASeptember 6, 2017 Page 41 of 50

or less and then resumed daily dosing with a dose reduction as outlined in Section 6.0.

8.4 Management of All Other Toxicities

Other toxicities may occur. Supportive care should be prescribed as needed. They may also be prescribed prophylactically to prevent toxicity from developing or recurring. The examples include anti-emetics for nausea/vomiting, analgesics for pain, antipyretics for fever and antidiarrheals for diarrhea

Abnormal laboratory values will be only be captured as adverse events if they are Grade 3 or higher.

8.5 Investigator Communication with Supporting Companies:

Within 24 hours of first awareness of the event (immediately if the event is fatal or lifethreatening, and related to study intervention), Principal Investigator will report to Novartis Pharmaceuticals by facsimile any Serious Adverse Event ("SAE," as defined below) that occurs from after the first dose of pazopanib through 30 days after discontinuation of pazopanib, using the M.D. Anderson Serious Adverse Event Form. Events should be reported as soon as they are determined to meet the definition, even if complete information is not yet available.

The SAE report should comprise a full written summary, detailing relevant aspects of the adverse events in question. Where applicable, information from relevant hospital case records and autopsy reports should be included. Follow-up information should be forwarded to Novartis Pharmaceuticals within 24 hours.

SAEs brought to the attention of the investigator at any time after cessation of pazopanib and considered by the investigator to be related or possibly related to pazopanib must be reported to Novartis Pharmaceuticals if and when they occur. Additionally, in order to fulfill international reporting obligations, SAEs that are related to study participation (e.g., procedures, invasive tests, change from existing therapy) or are related to a concurrent medication will be collected and recorded from the time the subject consents to participate in the study until he/she is discharged.

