The most common adverse events reported for pazopanib monotherapy to date are diarrhea, fatigue, nausea, hypertension, hair color changes (hair depigmentation), anorexia, vomiting, dysgeusia, headache, abdominal pain, rash, aspartate aminotransferase (AST) and alanine aminotransferase (ALT) increases, constipation, cough, and arthralgia. Most of these events were Grade 1 or 2 using the National Cancer Institute-Common Toxicity Criteria of Adverse Events, Version 4.0 (NCI-CTCAE, v4.0). The most frequent Grade 3 or 4 events were hypertension, fatigue, diarrhea, and AST and ALT increases. Less common AEs of note include hand-foot syndrome, mucositis/stomatitis, proteinuria, venous thrombotic events, and bleeding. Intestinal perforations and arterial thromboses were uncommon. The most common serious adverse events (SAEs), derived from all pazopanib studies that include studies where pazopanib was administered in combination with chemotherapy, are diarrhea, abdominal pain, vomiting, dyspnoea, hypertension (including one report of hypertensive crisis), pyrexia, anaemia, dehydration, fatigue, pneumonia, pleural effusion, neutropenia, pulmonary embolism, increase in ALT and nausea. Two cases of Torsades de Pointes have been reported in the pazopanib clinical program; however, whether or not there is a causal relationship to pazopanib remains unclear. A number of these events are known class effects of VEGF inhibitors. Therefore, this protocol is designed to closely monitor and provide clear management guidelines for these events based on the clinical experience with pazopanib to date.

2.3 Clinical and Preclinical Studies Assessing Response to Sunitinib in VHL, and Assessment of Endothelial Receptors in Renal Tumor and Hemangioblastoma Endothelium

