#### Specific recommendations regarding hypoglycemic therapy including insulin:

Results from drug-drug interaction studies conducted in subjects with cancer suggest that there will be no clinically relevant pharmacokinetic interaction between pazopanib and hypoglycemic agents. Transient decreases in serum glucose (mainly Grade 1 and 2, rarely Grade 3) have been observed in clinical studies with pazopanib. In addition, decreases in blood sugar have been recently reported in subjects treated with another small molecule

tyrosine kinase inhibitor, sunitinib. Such changes may require an adjustment in the dose of hypoglycemic and/or insulin therapy. Subjects should be advised to report symptoms of hypoglycemia (e.g., confusion, visual disturbances, palpitations, sweating). Serum glucose should be tested during treatment with pazopanib as outlined in the protocol and as clinically indicated.

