Grade 3 or 4	Step 1. Interrupt pazopanib until toxicity resolves to $\leq$ Grade 2.			
	Step 2. Restart pazopanib dose-reduced by 200 mg and monitor as clinically indicated.			
	If no recovery to $\leq$ Grade 2 or recurrent Grade 3 or 4 thrombocytopenia, discontinue pazopanib and follow-up per protocol			
Anemia: No specific dose reduction rules are indicated for anemia unless due to hemorrhage or bleeding as noted above.				
Other Clinically Significant Adverse Events b				
Grade 1	Continue pazopanib; monitor as clinically indicated.			
Grade 2 or 3, if clinically	Step 1. Interrupt pazopanib until toxicity resolves to $\leq$ Grade 1.			
significant	Step 2. Restart pazopanib dose-reduced by 200 mg and monitor as clinically indicated.			
Grade 4	Discontinue pazopanib and continue follow-up per protocol.			
Prolongation of QTc Interval: If the QTc is prolonged, the ECG should be manually read to ensure accuracy of the reading. The values below refer to manually-read ECGs.				
$QTc \ge 480 < 500 \text{ msec}$	Continue pazopanib; monitor as clinically indicated.			
QTc ≥500 msec	Discontinue pazopanib and continue follow-up per protocol.			

a. Well-controlled BP defined as SBP  ${<}140$  mmHg and mean DBP  ${<}90$  mmHg.

 b. AEs are graded according to NCI Common Terminology Criteria for Adverse Events v4.0 (NCI CTCAE v4)
 Abbraviations: PP, blood pressure

Abbreviations: BP, blood pressure.

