#### 8.0 ADVERSE EVENTS AND REPORTING REQUIREMENTS

8.1 Reporting Requirements

8.1.1 Adverse Drug Reaction Reporting

Toxicity will be scored using CTC Version 4.0 for toxicity and adverse event reporting. A copy of the CTC Version 4.0 can be downloaded from the CTEP homepage (http://ctep.info.nih.gov). All appropriate treatment areas have access to a copy of the CTC Version 4.0.

Adverse events will for this protocol will be documented and entered into the case report form according the Recommended Adverse event Recording Guidelines for Phase II protocol.

Protocol 2011-0465 ASeptember 6, 2017 Page 38 of 50

Table 8.					
Recommended Adverse Event Recording Guidelines					
Attribution	Grade 1	Grade 2	Grade 3	Grade 4	Grade 5
Unrelated	Phase I	Phase I	Phase I Phase II	Phase I Phase II Phase III	Phase I Phase II Phase III
Unlikely	Phase I	Phase I	Phase I Phase II	Phase I Phase II Phase III	Phase I Phase II Phase III
Possible	Phase I Phase II	Phase I Phase II Phase III			
Probable	Phase I Phase II	Phase I Phase II Phase III			
Definitive	Phase I Phase II	Phase I Phase II Phase III			

The Investigator or physician designee is responsible for verifying and providing source documentation for all adverse events and assigning the attribution for each event for all subjects enrolled on the trial.

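### Section 8.4 captures abnormal laboratory values as adverse events only from Grade 3 up, while 8.2 makes them reportable at any grade, and nothing reconciles the two

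*Combined protocol and SAP*

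**What the plan says.** **Capture of laboratory values.** Section 8.4 sets a grade floor: "Abnormal laboratory values will be only be captured as adverse events if they are Grade 3 or higher".

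Section 8.2 sets a different test. An abnormal result is reportable if any one of five criteria holds: accompanying symptoms; further testing or intervention; a consequence for dosing or other treatment; an outcome in the serious-event definition; or the investigator's judgement. The second criterion reads "Test result requires additional diagnostic testing or medical/surgical intervention, and/or" and the third "Test result leads to a change in study dosing or discontinuation from the study, significant additional concomitant drug treatment or other therapy, and/or". None mentions grade.

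Section 8.1.1 adds that adverse events "will be documented and entered into the case report form according the Recommended Adverse event Recording Guidelines for Phase II protocol". That guideline is Table 8, which has phase II trials record Grade 1 and 2 events of possible or stronger attribution.

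**Management.** Section 8.3 holds drug for any related toxicity above Grade 2. Once the event is Grade 1 or less, drug is resumed at a reduced dose, and Section 6.0 is cited for that reduction. Table 5 (Section 6.1) and Table 6 (Section 6.2) call for permanent discontinuation after certain severe events.

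**The concern.** Sections 8.2 and 8.4 answer the same question differently for any Grade 1 or 2 laboratory value that meets an 8.2 criterion. Staff who follow 8.4 will not enter it as an adverse event; staff who follow 8.2 will. The values at issue are those that had a consequence, because 8.2 selects on consequence or clinical judgement.

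Safety is part of the primary objective in Section 1.1, and Section 12.2 plans to estimate a toxicity rate with a 95% credible interval. If 8.4 is followed, the adverse-event data omit some clinically consequential laboratory toxicity, and the error runs towards understating toxicity. If practice varies, the data are also inconsistent from patient to patient.

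The 8.3 wording raises a lesser issue. Taken literally, it would resume drug after a recovered event that Tables 5 and 6 treat as the end of treatment.

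**Working it through.** No arithmetic applies to the main point. The check is to set the rules side by side and ask whether the protocol itself describes cases that fall between them.

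**Step 1. Is there a real gap?** The rows below follow from Sections 8.2 and 8.4, the glucose paragraph in 4.2.2, and Tables 5 and 6.

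| Laboratory event | Under 8.2 | Under 8.4 |
|---|---|---|
| Grade 2 glucose decrease leading to a change in insulin or hypoglycemic dose | Reportable (medical intervention) | Not captured |
| Clinically significant Grade 2 value with no row of its own in Table 5 | Reportable (dosing change) | Not captured |
| Grade 1-2 value that the investigator considers an adverse event | Reportable (fifth criterion) | Not captured |
| Grade 1-2 value with symptoms | Reportable (first criterion) | Value not captured; symptom still a clinical event |
| Grade 1-2 platelets, dose unchanged | Only if another criterion is met | Not captured |

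The first row is the protocol's own example. Section 4.2.2 says: "Transient decreases in serum glucose (mainly Grade 1 and 2, rarely Grade 3) have been observed in clinical studies with pazopanib". It then says: "Such changes may require an adjustment in the dose of hypoglycemic and/or insulin therapy".

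The second row rests on the entry in Table 5 for other clinically significant events. At Grade 2 or 3 it interrupts drug until Grade 1 or less, and then: "Restart pazopanib dose-reduced by 200 mg and monitor as clinically indicated". Creatinine and lipase illustrate this: Section 7.2.1 draws both every cycle and neither has its own row. A value can therefore change the study dose and never enter the adverse-event data.

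**Step 2. Which values are outside the gap?**
- Table 5 leaves the dose unchanged for Grade 1-2 platelets and for a urine protein to creatinine ratio below 3.
- Table 6 leaves it unchanged for ALT up to 8 x ULN without bilirubin elevation or hypersensitivity symptoms. Section 8.2 adds that repeating a test is not in itself enough for its second criterion.
- Liver chemistry events that meet the Section 6.2 definition are reported as serious adverse events whatever 8.4 says.

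**Step 3. Can the sections be reconciled?** One route treats 8.4 as a filter on 8.2, so that a value must meet both. That would cancel the dosing, intervention and investigator-judgement criteria below Grade 3, and 8.2 gives no hint of it. Another treats 8.4 as a laboratory exception to Table 8. That is tenable, which is why Table 8 is a secondary conflict and 8.2 the main one. Section 10.1 makes the principal investigator the arbiter of differing opinions on toxicity, but does not rank the sections.

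**Step 4. Can the size be found?** No. The documents say that glucose decreases are mainly Grade 1 and 2. Of the common adverse events in Section 2.2, a list that includes AST and ALT increases, they say: "Most of these events were Grade 1 or 2". They give no frequency for Grade 1-2 laboratory values that meet an 8.2 criterion.

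**Step 5. Section 8.3 against Tables 5 and 6.** Section 8.3 covers only related events above Grade 2. Within that range, the tables call for discontinuation where 8.3 literally resumes drug after recovery:
- Grade 3-4 hemorrhage
- Grade 4 venous thrombosis and/or pulmonary embolism
- Grade 3-4 arterial thrombosis (Table 5 says any grade; lower grades are outside 8.3)
- Grade 4 other clinically significant events
- Table 6 row D liver events, where these are above Grade 2 (row D is defined by multiples of ULN, and the protocol gives no grade cut-offs for ALT or bilirubin)

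The reference to Section 6.0 attaches to the dose reduction and does not exempt these rows.

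**The case against.** **On capture.** The strongest reply is that little is lost. Required laboratory results stay in the medical record, concomitant medication is recorded with dose, serious liver events are reported regardless, and symptoms are entered as clinical events. The glucose example concerns patients on hypoglycemic therapy, and Section 2.2 does not list creatinine or lipase abnormalities among the common effects of pazopanib. All of this stands and limits the consequence. It does not remove the contradiction. A value in the chart and a changed insulin dose do not amount to a graded, attributed adverse event.

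A reader might infer from the predominance of Grade 1 and 2 events that most of the liver signal would disappear. The documents do not support that. The statement covers the whole list of events, and most moderate ALT rises leave the dose unchanged, so they would often meet no 8.2 criterion either.

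**On management.** A reader might infer that the protocol directs re-exposure after a severe bleed or thrombosis. It does not. Section 8.3 is a general paragraph on persistent and refractory toxicity, its examples are events such as diarrhea and hypertension, and it points to Section 6.0. The tables give event-specific orders, and Table 6 allows re-challenge in row C but not in row D. Section 5.2 separately ends treatment for unacceptable adverse events. Priority for the tables is the natural reading. What remains is that it is not written, and that Section 6.1 introduces Table 5 as recommendations.

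**On the stopping rule.** Drug discontinuation due to toxicity is a formal stopping endpoint in Section 12.1, so a reader might infer that the early-stopping probabilities are affected. Capturing a laboratory value as an adverse event does not alter a count of discontinuations. For the 8.3 wording, the documents give no rate of disputed events that recover to Grade 1 or less, so no effect can be quantified.

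**Conclusion.** The conflict between 8.2 and 8.4 is real and should be corrected. Followed literally, 8.4 omits Grade 1-2 laboratory events that changed dosing, needed intervention or were judged adverse events by the investigator. The direction is towards under-reporting of toxicity; the size cannot be derived and is limited by the safeguards described above.

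This rests on two assumptions: that staff would apply 8.4 as written, and that the toxicity rate in Section 12.2 draws on adverse-event data. Section 12.2 does not define that rate. If it means only discontinuation due to toxicity, the omission would affect the description of safety and not that estimate.

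The mismatch between 8.3 and Tables 5 and 6 is a secondary drafting point. The intended priority is reasonably clear, and a sentence stating it is a cheap safety clarification.

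**What to change.** 1. Amend 8.4 to read: *Abnormal laboratory values are captured as adverse events if Grade 3 or higher, or at any grade if they meet a criterion in 8.2.* This keeps routine minor abnormalities out and brings the consequential ones in. It would still act as a laboratory exception to Table 8 for Grade 1-2 values that meet no 8.2 criterion, which is a reasonable choice.

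2. Add to 8.3: *Tables 5 and 6 govern wherever they give an event-specific or grade-specific instruction; the hold-and-resume rule applies only where they give none.*

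The cost is two sentences of protocol text, slightly more adverse-event entry and slightly higher reported toxicity. No new tests or visits are needed. The second sentence can add a discontinuation only where a patient would otherwise have been resumed under 8.3.

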### 9.0 CORRELATIVE/SPECIAL STUDIES

- 9.1 Correlate responders/nonresponders with genetic mutation analysis in order to define genetic signatures of responses at the organ level.
- 9.2 Baseline, week 12 and week 24 blood will be drawn and processed for cytokineangiogenesis factor analysis. A 50 panel Luminex bead based assay will be employed to evaluate baseline and therapy-induced changes in the profile. This profile will also be compared to internally generated data on patients with sporadic RCC to further explore the disease and therapy specificity of the profile.

9.3 Baseline, week 12 and week 24 blood will be drawn to evaluate baseline circulating endothelial cells and their changes as a function of therapy. These exploratory data will be employed to generate hypotheses on the interaction between host, tumor and therapy.

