## Table 1. Best Response of von Hippel-Lindau Lesions by RECIST after Sunitinib

Abbreviations: RECIST, Response Evaluation Criteria in Solid Tumors; NET, neuroendocrine tumors.

Of the 21 evaluable individual HB lesions, there were no partial responses (PR). In comparison, 6 of 18 RCC lesions responded with a PR, (P=0.014). All five pancreatic NETs responded with SD. None of the seven retinal angiomas demonstrated any shrinkage on ophthalmoscopy; however, two patients with retinal angiomas complained of increased hyperemia and eye discomfort during sunitinib treatment. When change in

Protocol 2011-0465 ASeptember 6, 2017 Page 10 of 50

lesion size was evaluated as a percentage by organ site per individual, RCC decreased a mean of 14.4% by the end of cycle four, NETs a mean 12.7%, and HB, 5.9% (Table 2). When size change was assessed as a continuous variable, both RCCs and NETs showed significant size decrease after four cycles of sunitinib therapy.

Forty-eight–week follow-up scans were obtained for renal lesions in five patients. In these patients, who had been finished with therapy for 6 months, RCC and NETs had regrown to close to baseline measurements but no larger (Table 2).

		Mean (Standard Error)						
	Baseline	Cycle 2	Percent	Cycle 4	Percent	Week 48	Percent	
Tumor Type	Size(cm)	Size (cm)	Change	Size (cm)	change	Size (cm)	change	
					-14.42		-3.37	
Renal Cell Carcinoma	2.41 (0.21)	2.04 (0.21)	-16.41 (3.9)	2.06 (0.22)	(4.5)	2.34 (0.24)	(5.7)	
P value		0.0004		0.0035		0.6098		
					-12.69		-1.72	
Pancreas NET	1.89 (0.28)	1.81 (0.28)	-3.59 (3.7)	1.64 (0.28)	(4.0)	1.89 (0.29)	(5.2)	
P value		0.284		0.011		0.959		
Hemangioblastoma	0.81 (0.08)	0.81 (0.08)	0.65 (3.4)	0.76 (0.08)	-5.9 (5.4)	0.76 (0.09)	-6.2 (5.4)	
P value		0.8	350	0.2	80	0.32	0	

Table 2. Mean Change from Baseline in Size of von Hippel-Lindau Lesions after Treatment with Sunitinib.	Table 2. Mean Change	e from Baseline	n Size of von	Hippel-Lindau	Lesions after	Treatment with Sunitinib.
---	----------------------	-----------------	---------------	---------------	---------------	---------------------------

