2.5 Rationale for choice of secondary endpoints

It may be difficult to measure success with an antiangiogenic agent using classical measures, such as RECIST, or progression free survival, due to the relative indolent rate of growth of some VHL related lesions. For that reason, we will request, where possible and available, that individuals who enroll on the study furnish imaging studies of their target VHL lesions up to 15 years prior to study enrollment. These studies will be used to generate a growth rate curve of target lesions, onto which the imaging studies acquired during the course of the study will be added. These data will provide information on the relative growth rates of VHL lesions, as well as how this growth rate is influenced by the chronic use of antiangiogenic therapy.

In a similar manner, we will acquire information on prior interventions performed on VHL related lesions in individuals treated on this study. We will calculate the rate of intervention over time, and determine whether this rate changes over the time period the patient is being followed.

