2.6 Rationale for choice of preclinical endpoints

Data on circulating cytokine and angiogenic factors suggest these factors provide important prognostic and potential predictive information in patients with RCC. Little is known about how these factors vary as a function of lesion type in VHL at baseline, and whether they predict for benefit from pazopanib therapy. We will collect circulating cells, plasma and sera from patients at baseline, after 12 weeks, 24 weeks and at time of study discontinuation.

It is not known whether specific VHL mutations are associated with response to pazopanib in VHL patients. We will perform exploratory analyses of the relationship between VHL genotype and response to therapy, both globally and according to specific lesion.

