### 12.2 Analysis Plans

If the trial is stopped early, this drug will not be considered of interest for future study VHL patients. If all 40 patients are accrued, we will estimate the response rate, early progression rate, toxicity rate and their corresponding 95% posterior credible intervals.

Biomarker endpoints and genetic mutations will be measured at baseline and/or over time. Summary statistics, including frequency tabulation, means, standard deviations, median, and range, will be used to describe subject characteristics and marker data. The chi-squared ( $\gamma^2$ ) test or Fisher's exact test will be used to test the association between two categorical variables, such as response and prognostic factors and discrete markers. The association among various continuous and discrete markers and response may be assessed first by the exploratory data analysis graphically and tested using Wilcoxon rank sum test. Correlation among continuous biomarkers will be examined by Pearson or Spearman rank correlation coefficients. Both univariate and multivariate logistic regressions may be performed to model the baseline prognostic factors such as age, gender, race, smoking history, performance status, markers, etc, on response, when appropriate. We will also use the generalized estimating equations to model correlated discrete variables. Repeated measures analysis including mixed effects model will be performed to analyze continuous biomarkers change over time. Time to progression (TTP) will be estimated using the Kaplan-Meier method. Log-rank test will be performed to test the difference in survival between prognostic groups. Regression analyses of survival data based on the Cox proportional hazards model will be

Protocol 2011-0465 ASeptember 6, 2017 Page 49 of 50

conducted on TTP. The proportional hazards assumption will be evaluated graphically and analytically, and regression diagnostics (e.g., martingale and Shoenfeld residuals) will be examined to ensure that the models are appropriate.

Table 2. Operating characteristics for the stopping rules for excessive PD rate or DD rate

True PD Rate	True DD Rate	Probability of	Average Expected #
		Early	of Patients
		Termination	
0.10	0.05	0.03	39.2
0.30	0.05	0.57	25.8
0.20	0.10	0.27	33.1
0.30	0.10	0.61	24.6
0.30	0.15	0.71	22.1
0.10	0.20	0.64	25.7
0.20	0.20	0.70	23.4
0.30	0.20	0.84	18.9
0.10	0.30	0.94	16.3

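### Genotype and marker analyses rest on responder status although per-organ size change is already measured: about 40–50% of the kidney information is discarded, and CNS and pancreas may offer little to compare

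*Combined protocol and SAP*

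**What the plan says.** Relating VHL genotype to pazopanib response is a stated objective (section 1.2). Section 2.6 describes it as "exploratory analyses of the relationship between VHL genotype and response to therapy, both globally and according to specific lesion". Section 9.1 makes this operational: "Correlate responders/nonresponders with genetic mutation analysis in order to define genetic signatures of responses at the organ level".

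Section 12.2 supplies the methods. Chi-squared or Fisher's exact test will "test the association between two categorical variables, such as response and prognostic factors and discrete markers". For the remaining marker analyses it says: "The association among various continuous and discrete markers and response may be assessed first by the exploratory data analysis graphically and tested using Wilcoxon". That is the two-sample test, with response as the grouping variable. Logistic regression on response may follow. Time to progression gets Kaplan-Meier, a log-rank test between prognostic groups and Cox regression. The mixed models in 12.2 are for biomarkers over time, not for tumour size.

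The underlying measurement is continuous. Section 11.1.5 sums lesion size separately for kidney, pancreas, CNS and retina and compares it with baseline. Section 7.2.1 schedules scans at the end of cycles 3 and 6, which are weeks 12 and 24. Partial response is a fall of at least 30% in that sum (11.3.1), confirmed no sooner than 6 weeks later (11.4.1).

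Two definitions of response are in force: CR+PR at 24 weeks in section 12.1, and CR+PR+SD in the notes to section 11.3.3. Section 9.1 does not say which it uses.

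**The concern.** The protocol's own background shows what the cut can hide. On sunitinib (section 2.3.1) there were no partial responses in 21 hemangioblastomas or in 5 pancreatic neuroendocrine tumours (NETs). On the measured scale, the same section reports: "When size change was assessed as a continuous variable, both RCCs and NETs showed significant size decrease after four cycles of sunitinib therapy". Section 2.5 makes the general point: "It may be difficult to measure success with an antiangiogenic agent using classical measures, such as RECIST".

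Section 2.4 predicts that pazopanib will do at least as well as sunitinib. If it does about as well, an organ-level comparison of responders with non-responders has few or no responders in CNS and pancreas, and in kidney it uses only part of the recorded data. With at most 40 patients, and fewer with disease in any one organ, a real genotype or cytokine association could easily be missed.

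**Working it through.** The documents state no power, error rate or effect size for these analyses, so there is no planned figure to reproduce.

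**Inputs from section 2.3.1.** Partial responses: hemangioblastoma 0/21, pancreatic NET 0/5, renal cell carcinoma (RCC) 6/18 = 33%. Mean change at cycle 4: RCC −14.42% (SE 4.5, P=0.0035); NET −12.69% (SE 4.0, P=0.011).

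**Assumptions.** The number of units behind the RCC standard error is not stated. With 18 lesions, SD = 4.5 × √18 = 19.1; with 9 units, SD = 4.5 × √9 = 13.5. Changes are normal, tests are two-sided at 5%, and two equal genotype or marker groups differ by 15 percentage points.

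**CNS and pancreas.** With no responders there is no 2×2 table to test. The two-sided 95% upper limit for the true rate is 1 − 0.025^(1/21) = 16% for 0/21 and 1 − 0.025^(1/5) = 52% for 0/5. Under CR+PR+SD the sunitinib split would be 19/21 in hemangioblastoma and 5/5 in NET. Two CNS non-responders give a best possible Fisher p of 0.21 at a 10:11 split, and NET has no contrast.

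**Kidney: information kept by the cut.** The efficiency of a cut relative to a normal measurement is φ(z)²/[p(1−p)], where p is the responder rate and z its normal quantile.
- The normal model gives p = Φ((−30 + 14.42)/19.1) = 0.207, so z = −0.817, φ = 0.286 and efficiency = 0.0817/0.164 = 0.50.
- At the documented p = 0.333: z = −0.431, φ = 0.364, efficiency = 0.132/0.222 = 0.59.
- With SD 13.5, p = 0.124 and efficiency = 0.39.

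The loss is therefore about 40–50% at responder rates of 21–33%, and about 60% at 12%.

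**Kidney: power.** The group means are −14.42 ± 7.5. The t-test uses the noncentral t distribution; Fisher's power is by exact enumeration. The cut is either the nominal −30%, or placed so that a third of patients respond overall, matching 6/18. With SD 19.1 and the −30% cut, for example, the responder rates are Φ((−30 + 21.92)/19.1) = 0.34 and Φ((−30 + 6.92)/19.1) = 0.11.

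| Groups | SD | t-test | Fisher, −30% cut | Loss | Fisher, 33% rate | Loss |
|---|---|---|---|---|---|---|
| 20 vs 20 | 19.1 | 0.68 | 0.28 | 59% | 0.35 | 48% |
| 20 vs 20 | 13.5 | 0.93 | 0.40 | 57% | 0.64 | 31% |
| 12 vs 12 | 19.1 | 0.45 | 0.12 | 74% | 0.18 | 61% |
| 12 vs 12 | 13.5 | 0.74 | 0.13 | 82% | 0.35 | 52% |

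Loss is 1 − Fisher/t-test, from unrounded powers.

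Fisher's test needs at least 5 responders, all in one of two equal groups, to reach p<0.05 (20 vs 20: p = 0.106 with 4, 0.047 with 5). Twenty kidney patients would yield about 4 to 7 responders (20 × 0.207 to 20 × 0.333).

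**Continuous marker.** For 18 to 30 patients, with a correlation giving Pearson on percent change about 80% power, simulated Wilcoxon power by responder status is 37–54%. That is a loss of 34–53%.

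**The case against.** The strongest reply is that these analyses are exploratory, carry no power claim, and alter no primary result or safety rule. Section 12.2 is worded permissively and does not bar an analysis of size change; growth rate is a secondary objective; and time to progression gives a route that does not use responder status. This stands as a limit on the weight of the point. It does not remove it: no analysis is written that links size change to genotype or markers, and progression is also a threshold event that was rare on sunitinib (2/21 hemangioblastomas, 2/18 RCC, 0/5 NET).

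A reader might infer that CNS and pancreas will have nothing to test. The documents do not support that as a certainty. It presumes CR+PR, it rests on best response per lesion to another drug, and 0/5 is compatible with a true rate of up to 52%. This trial uses per-patient organ sums with confirmation.

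A reader might also infer that well over half the kidney power is lost in general. That holds only over part of the range. At the documented 33% rate the Fisher loss can be as low as 31%. Uncorrected chi-squared, which 12.2 also names, loses 25–34% at that rate (equal groups, 16 to 40 patients, t-test power fixed at 80%). With 30:70 groups the Fisher loss runs from 23% to 98%, depending on which group responds. Kidney numbers are also unknown, since section 2.4 does not require RCC.

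Finally, responder status has a real advantage: section 12.1 counts early termination for progression or toxicity as failure, so those patients stay in the analysis. Size data may be missing for them, probably informatively, and the power figures above assume complete data.

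**Conclusion.** The point holds as a cheap improvement to exploratory analyses, not as a flaw in the primary evaluation. Apart from time to progression by prognostic group, the plan relates genotype and markers to tumour response through responder status while leaving a recorded continuous outcome unused.

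If pazopanib resembles sunitinib, the CR+PR contrast in CNS and pancreas is empty or nearly so, and CR+PR+SD rescues little. In kidney about 40–50% of the information is discarded at responder rates of 21–33%. Fisher's test loses about 31–61% of the t-test's power at the documented 33% rate, and about 57–82% with the −30% cut, where a normal model implies rates of only 12–21%. The power figures rest on the assumed 15-point difference, equal groups of 12 or 20, back-calculated SDs and normal changes. The direction of the loss does not depend on those exact values; its size does.

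**What to change.** In sections 9.1 and 12.2:
- Make percent change from baseline in the organ-specific sum of longest diameters, at weeks 12 and 24, the main outcome for the exploratory genotype and marker analyses. Fit kidney, pancreas and CNS separately with a linear mixed model containing baseline sum, visit, genotype or marker, and a patient random effect. Add a rank-based check.
- Keep responder status as supportive, and state whether those tables use CR+PR (12.1) or CR+PR+SD (11.3.3). The two sections must be reconciled.
- State how early stopping and new lesions are handled, for example by a rank analysis that gives the worst rank to patients who stop early for progression or toxicity or who develop new lesions.

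The cost is a few sentences and modest programming, with no new data, visits or patients. Some size data will still be missing after early stopping, new lesions do not enter the target sum (hence the worst-rank rule), and results are read as percentage points instead of odds. The 24-week CR+PR efficacy endpoint does not change.
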